4.5.3 Prohibited Medications/Treatments

The decision to administer a prohibited medication/treatment is done with the safety of the study participant as the primary consideration. When possible, Allergan should be notified before the prohibited medication/treatment is administered.

The following medications should be avoided during the study:

- SE-intravitreal injections of any sort other than the study medication
- SE-sub-tenon, subconjunctival or topical corticosteroids

- systemic corticosteroids (oral, inhaled, intranasal, intravenous, intramuscular, epidural, rectal, or extensive dermal); for patients who are assigned to DEX PS DDS drug monitoring any form of dexamethasone should be avoided during the first 6 months.
- systemic anti-VEGF therapies
- systemic immunosuppressants, immunomodulators, antimetabolites or alkylating agents
- systemic carbonic anhydrase inhibitors (eg Diamox)
- SE-additional invasive nonstudy procedures or surgery

If the permissibility of a specific medication/treatment is in question, please contact Allergan.

5. Study Treatments

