5.3 Escape Therapy

Treatment according to standard of care (SOC) should be considered for patients with a decrease of BCVA > 10 ETDRS letters from baseline, which is confirmed at 2 consecutive visits. Patients who receive escape therapy will no longer eligible to receive study treatment, but will continue in the study for safety assessments.

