7.3.1 Primary Efficacy Analyses

The primary efficacy endpoint is the average change from baseline in BCVA in 12 months. The primary analysis will be an analysis of covariance (ANCOVA) comparing the treatment difference in the mean average BCVA change from baseline over a 12-month study period. The ANCOVA model will include the treatment group as the main effect and baseline BCVA score as the covariate.

The null hypothesis is that there is no difference between 700-µg DEX PS DDS and laser in the average BCVA change from baseline in a 12-month period. The alternative hypothesis is that there exists a difference between the 2 treatment groups. The hypothesis test will be based on a 2-sided test at 0.05 significance level. In addition, a 2-sided 95% confidence interval (CI) will be constructed for the difference between the treatment groups in least-square means using the same ANCOVA model. Data collected after receiving any prohibited or standard of care treatments will be excluded from all the efficacy analysis.

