ATC	Anatomical Therapeutic Chemical
AUC	Area under the curve
BCVA	Best corrected visual acuity
CFB	Change from baseline
CI	Confidence interval
CMH	Cochran-Mantel-Haenszel
CRT	Central retinal thickness
D	Day
DEX PS DDS	Extruded dexamethasone posterior segment drug delivery system
DME	Diabetic macular edema
ETDRS	Early treatment diabetic retinopathy study
Ecrf	Electronic case report form
FA	Fluorescein angiography
IOP	Intraocular pressure
LS	Least squares
M	Month
MedDRA	Medication Dictionary for Regulatory Activities
mITT	Modified intent-to-treat
OCT	Optical coherence tomography
OU	Both eyes
PE	Physical examination
PP	Per-protocol
PT	Preferred term
SAE	Serious adverse event
SAP	Statistical analysis plan
SD	Standard deviation
SE	Standard error
SE	Study eye
SOC	System organ class
TEAE	Treatment-emergent adverse event
VA	Visual acuity
VFQ	Visual functioning questionnaire
WHO	World Health Organization

700 µg DEX PS DDS

1. Introduction

This statistical analysis plan (SAP) details comprehensive, technical specifications of the statistical analyses of the efficacy, safety data and health outcomes outlined or specified in the final protocol of Study 206207-026 amendment 1. Specifications of tables, figures, and data listings are contained in a separate document.

Study 206207-026 is a Phase 3, multicenter, randomized, 12-month comparative study. This study is conducted to evaluate the safety and efficacy of the 700 µg DEX PS DDS compared with laser photocoagulation in participants with diabetic macular edema (DME). This is a regional multicenter Phase 3 registration trial and is conducted exclusively in China and The Philippines.

[figure not shown]

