2.3 Data Conventions

- Unless stated otherwise in specific subsequent sections, data conventions and definitions listed below will be applied to all analyses. Study duration will be calculated for each participant as:

Study duration = date of the last visit – date of the 1st study treatment + 1

- In general, study day of a visit/assessment/treatment/event/procedure (i.e., BCVA assessment, escape therapy) will be calculated as below.

If the visit date is on or after the 1st study treatment, study day will be calculated as:

Study Day = visit date – date of the 1st study treatment + 1

Day 1 is the day of the 1st study treatment

If visit date is before the 1st study treatment, study day will be calculated as:

Study Day = visit date – date of the 1st study treatment

Day -1 is the day before the 1st study treatment

- Unless otherwise specified, baseline data refer to assessments performed at the Baseline (Day 1) visit prior to the first treatment. Screening or unscheduled but prior to Day 1 visits can be used for baseline in the absence of pertinent data at the baseline visit.
- For continuous variables, descriptive statistics will include mean, median, standard deviation, 25-percentile, 75-percentile, minimum and maximum. Descriptive summary for the categorical data will be count and percentage for each category.
- The Medical Dictionary for Regulatory Activities (MedDRA) nomenclature will be used to code adverse events, biomicroscopy, and ophthalmoscopy findings.
- The Anatomical-Therapeutic-Chemical classification text from World Health Organization (WHO) Drug Dictionary will be used to code all medications for drug class and for drug name.
- All data will be listed.

700 µg DEX PS DDS

- Data after the escape therapy will be excluded from efficacy analyses and will be included in safety analyses. Since assessments (e.g., BCVA, CRT) are usually performed before any treatments (e.g., study treatment, escape therapy), data collected on the same day but prior to the escape therapy will be included in analysis.
- Due to IP recall during the study, a small number of participants have delayed Ozurdex treatment at Month 12. It is recommended that these participants can come back 2 months after the last treatment for a follow-up visit. Therefore, data collected up to day 450 will be used in efficacy analysis. However, all data during the study will be included in safety analysis.

3. Disposition and Exit Status

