5.1 Primary Efficacy Analyses

5.1.1 Collection of Primary Efficacy Measurements and Derivation of Primary Efficacy Variable

BCVA is measured using the Early Treatment Diabetic Retinopathy Study (ETDRS) method. The number of letters read correctly will be recorded.

The primary endpoint is the average change from baseline in BCVA in study eye over the 12-month study period for each participant. The average BCVA will be calculated as the area under the BCVA curve divided by the study days at the last BCVA measurement of the study eye over the 12-month study period.

Change from baseline = average BCVA – Baseline BCVA.

The area under the BCVA curve will be calculated using the trapezoidal method and will include all BCVA data, regardless of scheduled or unscheduled visits, from day 1 to the last BCVA assessment prior to escape therapy or at exit visit. The total area under the BCVA curve can be partitioned into sub-areas divided by consecutive visits that each participant had with BCVA measurements. For a particular participant, assume that BCVA is obtained at L

time points (visits) including the baseline visit. Let t_i and $BCVA_i$ represent the study day and BCVA value at Visit i (e.g., baseline/day 1, month 1, etc.), respectively, and

$t_i = t_1, t_2, \dots, t_L$, where $t_1 = \text{day 1 (baseline)}$ and,

$t_L = T$ (month 12 or time at the last BCVA if early term inated or at the 1st escape therapy)

The total area under the BCVA curve over $[1, T]$ study days:

$$AUC_{[1,T]} = \sum_{i=1}^{L-1} AUC_i(t_i, t_{i+1}), \text{ where } AUC_i = (BCVA_{t_{i+1}} + BCVA_{t_i}) * (t_{i+1} - t_i) / 2$$

The average BCVA for the participant = $\frac{1}{T-1} AUC_{[1,T]}$, and

The average BCVA change for the participant = $\frac{1}{T-1} AUC_{[1,T]} - BCVA_{\text{baseline}}$

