5.2 Secondary Efficacy Analyses

Data after the 1st escape therapy will be set to missing. For participants who receive escape therapy or terminate early prior to month 12, month 12 data will be imputed using LOCF (Last Observation Carry Forward). The last observation prior to the 1st escape therapy or at early exit will be used for month 12. In the event of mis-randomization with an incorrect stratum, the actual stratum that the participant belongs will be used for statistical analysis.

5.2.1 BCVA Improvement of ≥ 15 Letters from Baseline at month 12

[figure not shown]
Analysis for proportion of participants with 15 or more letters improvement from baseline in BCVA of study eye at month 12 will be done using a Cochran–Mantel-Haenszel (CMH) test stratified by baseline BCVA categories (≥ 34 to ≤ 49 and ≥ 50 to ≤ 70). The 95% confidence intervals for the between-group difference in the proportion will be calculated using normal approximations.

5.2.2 Change from Baseline in Central Retinal Thickness at Month 12

Analysis for change from baseline in central retinal thickness measured by OCT at month 12 will be performed using an ANCOVA model with treatment and baseline BCVA category as the main effects and baseline retinal thickness as the covariate. The between-group difference and the corresponding 2-sided 95% CI in least-square means will be computed using the ANCOVA model.

5.2.3 Change from Baseline in Total Leakage Area at Month 12

The total area of macular leakage measured by FA is defined as the sum of focal and diffuse leakage area. Analysis for change from baseline in total leakage area at month 12 will be performed using an ANCOVA model with treatment and baseline BCVA categories as the main effects and baseline total leakage area as the covariate. The between-group difference and the corresponding 2-sided 95% CI in least-square means will be computed using the ANCOVA model.

6. Safety Analyses

The safety analysis will be based on safety population using observed data.

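### The protocol ends efficacy data at any prohibited or standard of care treatment; the readable SAP ends it only at escape therapy and does not explain the difference

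*Protocol*

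**What the plan says.** Protocol 7.3.1, in the text on the primary analysis, sets a rule for every efficacy analysis: "Data collected after receiving any prohibited or standard of care treatments will be excluded from all the efficacy analysis".

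The SAP introduction says that it specifies the analyses "outlined or specified in the final protocol of Study 206207-026 amendment 1". Its own rules on treatment received during follow-up are narrower:

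- SAP 2.3: "Data after the escape therapy will be excluded from efficacy analyses and will be included in safety analyses". Assessments made on the same day but before escape therapy are kept.
- SAP 5.1.1: the area under the BCVA curve runs "from day 1 to the last BCVA assessment prior to escape therapy or at exit visit".
- SAP 5.2, for the secondary endpoints: "Data after the 1st escape therapy will be set to missing". It continues: "For participants who receive escape therapy or terminate early prior to month 12, month 12 data will be imputed using LOCF".

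The only other limits in the SAP are exit and day 450. SAP 2.3 justifies day 450 by the product recall.

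Escape therapy comes from protocol 5.3: "Treatment according to standard of care (SOC) should be considered for patients with a decrease of BCVA > 10 ETDRS letters from baseline", with the loss confirmed at two consecutive visits. Prohibited treatments are a separate list in protocol 4.5.3 with no vision criterion. One item is "SE-intravitreal injections of any sort other than the study medication". That section accepts that such treatment may be given when a participant's safety calls for it.

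**The concern.** The primary endpoint is each participant's BCVA averaged up to a cut-off, less baseline. The cut-off decides which measurements enter the average and also sets the divisor. If two governing documents give two cut-offs, the same records can produce two primary values for one participant.

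The primary analysis uses the mITT population, so the supportive per-protocol run in SAP 5.1.3 does not settle which rule applies. Investigators know the assignment (protocol 9.4). A cut-off that depends on treatments they choose should therefore be stated once, and before the data are unmasked.

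**Working it through.** **Comparing the rules**

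| Place | Treatment that ends efficacy data |
|---|---|
| Protocol 7.2.1 (definition of the primary variable) | None stated; runs to the last measurement |
| Protocol 7.3.1 (all efficacy analyses) | Any prohibited or standard of care treatment |
| SAP 2.3, 5.1.1, 5.2 | Escape therapy only |

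Applying 7.3.1 and the SAP to four situations:

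1. Escape therapy after a confirmed loss of more than 10 letters: both cut. No conflict.
2. A 4.5.3 treatment not recorded as escape therapy: 7.3.1 cuts, the SAP does not. This is the conflict.
3. Standard of care treatment for DME in the study eye after a smaller loss: 7.3.1 cuts. The SAP result depends on whether the site records it as escape therapy, because the readable SAP attaches no letter threshold to the term.
4. Treatments on which 4.5.1 and 4.5.3 overlap (inhaled or intranasal steroids; cataract surgery, if it counts as additional study-eye surgery): 7.3.1 is unclear until the plan says which section governs. Assigned laser also needs a statement, because protocol section 1 calls laser the standard of care for DME in China.

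**Size for one participant**

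The documents give no figure to reproduce, so this is an illustration of situation 2.

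- Formula (SAP 5.1.1): average change = AUC over days 1 to T, divided by (T − 1), minus baseline. Working in change from baseline, baseline is 0.
- Days (SAP Table 2-1 targets): 1, 30, 60, 90, 150, 180, 210, 270, 300, 360.
- Assumptions: change is 0 at day 1 and −4 letters from day 30 to the treatment visit. A non-study injection, not recorded as escape therapy, follows that visit's BCVA. From the next visit on, the eye is at +1, −4 or −9. None of these meets the 5.3 criterion.

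Value under 7.3.1 (cut at the treatment visit). The first 29 days contribute −4 × 29/2 = −58.

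- Day 90: (−58 − 4 × 60)/89 = −298/89 = −3.35
- Day 180: (−58 − 4 × 150)/179 = −658/179 = −3.68
- Day 270: (−58 − 4 × 240)/269 = −1018/269 = −3.78

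Value under the SAP (to day 360, divisor 359):

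- Treated at day 90: to +1, (−298 − 90 + 210)/359 = −0.50; to −9, (−298 − 390 − 1890)/359 = −7.18
- Treated at day 180: to +1, (−658 − 45 + 150)/359 = −1.54; to −9, (−658 − 195 − 1350)/359 = −6.14
- Treated at day 270: to +1, (−1018 − 45 + 60)/359 = −2.79; to −9, (−1018 − 195 − 540)/359 = −4.88
- Stays at −4, any day: (−58 − 4 × 330)/359 = −1378/359 = −3.84

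SAP value minus 7.3.1 value, in letters:

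| Treated at | Gains 5 (to +1) | Stays at −4 | Loses 5 (to −9) |
|---|---|---|---|
| Day 90 | +2.85 | −0.49 | −3.83 |
| Day 180 | +2.14 | −0.16 | −2.46 |
| Day 270 | +0.99 | −0.05 | −1.10 |

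A different assumed path gives other values. An eye with no change to month 6 that then gains 5 letters has 0 under 7.3.1 and (75 + 750)/359 = +2.30 under the SAP.

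**Size for an arm**

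The shift in an arm mean is the share of participants affected times their mean difference. The documents give neither, so no arm-level figure follows.

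**The case against.** - **An early rescue injection may count as escape therapy.** Protocol 5.3 says when standard of care should be considered. It does not say that treatment given sooner falls outside the term, and the readable SAP sets no threshold. This stands. A reader might infer that the SAP keeps vision data after every DME injection given before a confirmed loss of more than 10 letters, but the documents do not show that. The conflict is limited to treatment not recorded as escape therapy.
- **The protocol is not aligned with itself.** Section 7.2.1 has no treatment cut-off, so the SAP lies between two protocol sections. This also stands, and the protocol needs a cross-reference. It does not remove the conflict, since 7.3.1 is the specific exclusion and covers all efficacy analyses.
- **Redacted or separate text may reconcile the rules.** The PP definition (SAP 2.1) and a block after SAP 8.2 are redacted, and deviations are classified in a separate document (SAP 3.2). A reader might infer that the sponsor dropped the clause without giving a reason. The documents support only that no readable text gives one. A PP definition could not change the mITT data in any case.
- **The missing imputation rule might look like a second defect.** It is not. Under the SAP alone, a participant with a prohibited treatment keeps the observed month 12 value. The gap in SAP 5.2 appears only once the 7.3.1 cut is applied.
- **Keeping more data may be preferable.** Retaining the SAP rule and recording the departure would also resolve the inconsistency. That is a fair alternative, and the fix allows for it.

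**Conclusion.** The inconsistency in the readable text is certain: following the SAP as written departs from a stated protocol rule on the primary mITT endpoint. Whether the departure is explained elsewhere cannot be determined.

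For an affected participant, the choice of rule can move the primary value by several letters in either direction. That size rests on the assumed vision paths, visits on target days and a treatment not recorded as escape therapy.

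A reader might infer that the SAP rule favours one arm, since investigators are unmasked and use of other treatment could differ by arm. The documents give no rate of prohibited treatment and no direction of effect, so they do not support that inference. The point is of moderate weight and should be settled before unmasking.

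**What to change.** 1. In SAP 2.3, 5.1.1 and 5.2, end efficacy data at the earlier of first escape therapy and first treatment prohibited by protocol 4.5.3, as 7.3.1 requires. Define escape therapy to include any standard of care DME treatment of the study eye, whatever the letter loss. Keep same-day assessments made before the treatment.
2. State that treatments expressly permitted by protocol 4.5.1 (cataract surgery, inhaled or intranasal steroids, panretinal photocoagulation) and assigned laser under 5.7.2 are not cut-off events.
3. Apply the existing LOCF rule in SAP 5.2 to participants cut in this way.
4. Cross-refer protocol 7.2.1 to 7.3.1.
5. Finalise the cut-off derivation before unmasking.
6. Rerun the primary ANCOVA with the escape-only cut-off as a sensitivity analysis. If the sponsor prefers that cut-off as primary, record it as a departure from 7.3.1 with its reason, and run the 7.3.1 rule as the sensitivity analysis.

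The cost is wording in three SAP sections, one protocol cross-reference, one date derivation from the medication and procedure records that SAP 4.4 already summarises, and one extra ANCOVA. No new data or visits are needed, and nobody's treatment changes. The downside is shorter efficacy follow-up for affected participants, whose number is unknown; 7.3.1 already requires this.

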7.3.2 Secondary Efficacy Analyses

Analysis for proportion of patients with 15 or more letters improvement from baseline in BCVA at month 12 will be done using a Cochran–Mantel–Haenszel (CMH) test stratified by baseline BCVA categories (≥ 34 to ≤ 49 and ≥ 50 to ≤ 70) within each study site.

Analysis for change from baseline in retinal thickness at month 12 will be performed using an ANCOVA model with treatment and baseline BCVA score (≥ 34 to ≤ 49 and ≥ 50 to ≤ 70) as the main effects and baseline retinal thickness as the covariate. The between-group difference and the corresponding 2-sided 95% CI in least-square means will be computed using the ANCOVA model. The within-group change from baseline will be analyzed using the paired t-test at the follow-up visits.

Analysis for change from baseline in total leakage area at month 12 will be performed using an ANCOVA model with treatment and baseline BCVA score (≥ 34 to ≤ 49 and ≥ 50 to ≤ 70) as the main effects and baseline total leakage area as the covariate. The between-group difference and the corresponding 2-sided 95% CI in least-square means will be computed using the ANCOVA model. The within-group change from baseline will be analyzed using the paired t-test at the follow-up visits.

[REDACTED]

7.3.4 Safety Analyses

The Medical Dictionary for Regulatory Activities (MedDRA) nomenclature will be used to code adverse events and biomicroscopy data.

The number and percent of patients reporting adverse events will be tabulated by primary system organ class, preferred term, and severity for adverse event summarization. The summary tables will be generated separately for adverse events reported during the screening to baseline period (pre-adverse event) and treatment emergent period. Summaries for treatment-emergent adverse events will be organized into the following: all adverse events regardless of causality; treatment-related adverse events; ocular adverse events in the SE; and treatment-related ocular adverse events in the SE.

[REDACTED]

[REDACTED]

[REDACTED]

[REDACTED]

[REDACTED]

7.5 Interim Analyses

No interim analysis is planned for this study.

8. Study Visit Schedule and Procedures

The total duration of study participation for each patient is approximately 12.5 months, including screening and randomization/retreatment period. Patients will attend the following

11 visits: screening visit, randomization visit, 8 assessment/retreatment visits, and study exit visit. Please see Table 1 and Figure 1 for a schematic of the schedule of visits and procedures.

8.1 Patient Entry Procedures

8.1.1 Overview of Entry Procedures

Prospective subjects as defined by the criteria in Sections 4.3 and 4.4 (inclusion/exclusion criteria) will be considered for entry into this study. Prior to patient randomization, patient eligibility must be reviewed and confirmed.

8.1.2 Informed Consent

The study will be discussed with the patient, and a patient wishing to participate must give informed consent prior to any study-related procedures or change in treatment. Each patient that provides informed consent will be assigned a patient number that will be used on patient documentation throughout the study.

[REDACTED]

[REDACTED]

[REDACTED]

[REDACTED]

[REDACTED]

[REDACTED]

[REDACTED]

[REDACTED]

[REDACTED]

[REDACTED]

[REDACTED]

[REDACTED]

[REDACTED]

[REDACTED]

[REDACTED]

[REDACTED]

700 µg DEX PS DDS

| [REDACTED]

| [REDACTED]

| [REDACTED]

| [REDACTED]

| [REDACTED]

| [REDACTED]

| [REDACTED]

| [REDACTED]

| [REDACTED]

[REDACTED] [REDACTED]

| [REDACTED]

| [REDACTED]

| [REDACTED]

| [REDACTED]

| [REDACTED]

| [REDACTED]

| [REDACTED]

| [REDACTED]

| [REDACTED]

| [REDACTED]

| [REDACTED]

700 µg DEX PS DDS

[Redacted]

[Redacted]

[Redacted]

[Redacted]

[Redacted]

[Redacted]

[Redacted]

[Redacted]

[Redacted]

[Redacted]

[Redacted]

[Redacted]

[Redacted]

[Redacted]

[Redacted]

[Redacted]

[Redacted]

[Redacted]

[Redacted]

[Redacted]

1 [Redacted]

1 [Redacted]

1 [Redacted]

1 [Redacted]

1 [Redacted]

1 [Redacted]

1 [Redacted]

1 [Redacted]

[Redacted]

1 [Redacted]

1 [Redacted]

[Redacted]

[Redacted]

1 [Redacted]

1 [Redacted]

1 [Redacted]

1 [Redacted]

1 [Redacted]

1 [Redacted]

1 [Redacted]

1 [Redacted]

700 µg DEX PS DDS

[REDACTED]

[REDACTED]

[REDACTED]

[REDACTED]

[REDACTED]

[REDACTED]

[REDACTED]

[REDACTED]

[REDACTED]

[REDACTED]

[REDACTED]

[REDACTED]

[REDACTED]

[REDACTED]

[REDACTED]

[REDACTED]

[REDACTED]

[REDACTED]

[REDACTED]

[REDACTED]

700 µg DEX PS DDS

[REDACTED]

[REDACTED]

[REDACTED]

[REDACTED]

[REDACTED]

[REDACTED]

[REDACTED]

[REDACTED]

[REDACTED]

[REDACTED]

[REDACTED]

[REDACTED]

[REDACTED]

[REDACTED]

[REDACTED]

[REDACTED]

[REDACTED]

[REDACTED]

[REDACTED]

700 µg DEX PS DDS

[REDACTED]

[REDACTED]

[REDACTED]

[REDACTED]

[REDACTED]

[REDACTED]

[REDACTED]

[REDACTED]

[REDACTED]

[REDACTED]

[REDACTED]

[REDACTED]

[REDACTED]

[REDACTED]

[REDACTED]

[REDACTED]

[REDACTED]

